### ***Patients***

We will interview 10 patients at each participating unit assigned to the intervention for a total of 50 patient interviews. During the intervention period, the site Research Assistant will work with unit staff to identify and approach patients. The RA will discuss with unit staff to determine if it is appropriate to approach a patient based on his/her health needs and other contextual factors; for example, patients will not be approached who are receiving end-of- life care, are cognitively impaired, or are unable to understand English. Patients who are under contact precaution isolation above and beyond the intervention (for example, use of gowns and gloves for all patient contact) will not be approached for interviews. We will work with unit staff to refine the process for identifying patients who may be approached as needed based on unit staff's preferences; for example, members of the healthcare team may wish to make first contact with a patient –by asking if they may introduce the RA to discuss a research opportunity or by distributing flyers describing the interviews prior to the RA visit to the unit. The healthcare team member will not screen for eligibility or directly recruit patients to participate in interviews. Rather, the healthcare team member's role is to facilitate patient care by being an advocate for the patient.

The RA will check with the patient's nurse or other healthcare team member before approaching the patient to ask him/her to participate and will not approach any patient without the nurse's or other healthcare team member's agreement that it is a good time to do so. The RA will not approach patients who have indicated they do not want to be contacted, receiving end-of-life care, cognitively impaired, non- English speakers, in contact isolation precautions or when he/she is undergoing any medical procedures. The RA will ask the patient in his/her room if he/she is willing to speak about a voluntary research opportunity. If so, the RA will meet face-to- face with the patient to assess eligibility and to provide basic information regarding the study and the voluntary nature of participation. A liberal amount of time will be allotted for discussion of the study and the patient's role in the study, and to answer any questions posed by the patient. The written information sheet will also be provided to the patient. The RA will offer the potential subject time for private contemplation and review of the documents provided or time to discuss the study with important support persons not currently with the patient. If the patient decides to participate, he/she can tell the RA in person or via the provided contact information in order to set up an interview. The RA will ask for the patient's phone number so that the

patients can be contacted regarding the interviews. In addition, the RA will ask the patient if the RA may return to the patient at a later time to check in about their decision. The RA may return to the patient one additional time to follow-up, and only with the patient's approval to do so based on the recruitment script. Patients who agree to participate in interviews will be given a brief, voluntary, anonymous demographics survey by the local RA (e.g., with the interview information sheet) to complete before or after the interview. Patients may participate in interviews even if they decline to complete the demographics survey.

## **SURVEYS**

### *Patients*

We will work with unit staff to refine the process for identifying patients who may be approached as needed based on unit staff's preferences; for example, the healthcare team member may wish to make first contact with a patient –by asking if they may introduce the RA to discuss a research opportunity or by distributing flyers describing the survey prior to the RA visit to the unit. The healthcare team member will not directly recruit patients to participate in the surveys. The RA will check with the patient's nurse before approaching the patient to ask him/her to participate and will not approach any patient without the nurse's agreement that it is a good time to do so. We will recruit patients to complete a Patient-Provider Contact Survey to understand perceptions of whether contact with patients is impacted due to the intervention. No PII or PHI will be included on these surveys. We will aim to obtain 10 patient surveys per site.

We will work with unit staff to determine how to share the survey with patients; options may include leaving the survey on bedside table, including survey in admission/discharge paperwork, and/or having research staff explain the survey and ask patient if they are willing to participate. A pen/pencil will be provided to patients who wish to complete the survey. We will collect completed surveys through a discreet, anonymous receptacle and/or the RA picking up surveys from patients who have agreed to complete the survey.

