## 4.1 Resources and Personnel

### 4.2 Participating Sites

The coordinating study site and personnel (including the PI) will be based at the Madison VA. The Madison VA-based team will be responsible for overall study execution, including protocol refinement, comprehensive site training, medical monitoring, handling of patient-related issues that may arise, coordination of clinical event ascertainment efforts, and interfacing with study committees and local site teams.

Five sites (Milwaukee, Hines, Bronx, Washington DC, Portland) will enroll ten inpatient units (i.e., acute medical, medical/surgical, surgical or specialty units) to participate in the study; 2 inpatient units at each site. A Local Site Investigator (LSI; see above list of names under personnel) and a Research Assistant (RA) will be assigned to each participating site to assist in completing study procedures and ensuring compliance with the study protocol at this site.

Local site responsibilities will be discussed in detail with the LSI and RA prior to beginning study procedures. These responsibilities may include:

- Maintain site documentation (e.g. study binder, study information sheets, sample code key)
- Obtain local approvals as required

- Ensure adherence to study protocol and procedures
- Provide education/training on study procedures for local staff and on-site resource for staff and patient questions
- Recruit patients and consent for swab/stool sample collection
- Specimen collection
  - Stool samples – collect swab/stool specimens,
  - provide supplies and instructions to patients performing self-collected specimen collection,
  - specimen label, store, ship
- Collect data
  - intervention fidelity
  - Clinical outcomes
- Upload data to Madison
- Recruit patients and healthcare workers for interviews/focus groups
- Facilitate and/or Conduct patient interviews
- Facilitate and/or Conduct healthcare worker focus groups
- Conduct observations of hand hygiene, contact precaution, and universal gloving practice compliance
- Recruit patients and healthcare workers for surveys
- Organize survey collection process
- Participate in meetings/check-ins with coordinating site; maintain communication
- Follow all VA privacy/information security regulations

Clinical staff (such as nursing staff) will also assist with study conduct. Clinical staff's responsibilities may include:

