### **5.2.3 Study Population**

The study population will be ten participating units. All patients aged 18 and above within these units will be included in the intervention and clinical data collection.

Within the units assigned to the intervention, we will conduct interviews with healthcare workers and patients about their experiences with the intervention. We will conduct focus groups with up to 60 healthcare workers (up to 12 individuals for each of the 5 sites enacting the intervention) who are aged 18 and above, are employed by the participating facility and have performed employment duties within the participating unit during the intervention period, and who agree to participate in the interview. We will interview 50 patients (10 per site enacting the intervention) who are aged 18 and above, are admitted as an inpatient to the participating unit during the intervention period, and who agree to participate in the interview.

We will also conduct surveys with patients and environmental services staff. We will aim to survey 10 patients per site at all 10 participating sites, for a total of 100 patients (50 from intervention group and 50 from control group). Given the small expected number of environmental service staff on each unit, we will aim to survey at least 1 worker per site at all 10 participating sites, for a total of 10 workers.

Focus groups and patient interviews will be conducted via face-to-face or phone/Teams call. All interviews will be audio-recorded to be transcribed later for analysis of themes and concepts unless patients decline to be recorded, in which case field notes will be taken and analyzed instead. Please see section 7.0 for specific detailed procedures for handling interview recording and transcript information.

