### **Survey**

**Provider-Patient Contact:** Surveys of patients will be used to assess perception of provider-patient contact and patient satisfaction with this contact. Survey results will be compared between the control or intervention group to determine if the intervention may be impacting patient satisfaction with their care. Surveys will be conducted during the patient's stay in the unit and may be returned to any member of their care team or left at the nurse's station upon

discharge. The local research assistant will collect all surveys for analysis.

**Environmental Services Experience:** Healthcare workers in environmental services will be surveyed to determine if the additional use of gloves in the unit may be impacting workflow/workload (for example, by increasing the frequency of trash disposal required on the unit). Surveys may be returned to a secure location (e.g. a drop box) and the local research assistant will collect all surveys from this location for analysis.

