### **5.7 Safety Monitoring**

This study poses minimal risk to participants. To ensure the safety of healthcare workers and patients in participating units we will use regularly collected VA quality and safety metrics. Metrics that are regularly collected by VA that will be monitored here may include information on falls, hand hygiene compliance, contact precaution/personal protective equipment use compliance, and patient satisfaction (e.g. SHEP scores). Hand hygiene and contact precaution/personal protective equipment use compliance data from observations conducted as part of our research will be complemented with standard data collected by infection control to monitor for changes in adherence to infection control practices.

[figure not shown]
We will work with the LSI and RA at each site to develop a site-specific plan for transmitting these metrics, i.e., whether the Madison study team will download these aggregate data from the Corporate Data Warehouse or whether the local study team will upload these data to the Madison study team using VA-secure methods behind the VA firewall. The Provider-Patient Contact survey will also be used to monitor patient responses to the intervention and ensure that the universal gloving practices are not causing a negative impact on patient experience.

Given the minimal risks posed by this study, we do not anticipate that any safety conditions will trigger suspension of the study. If we find significant negative impacts, we will notify the site LSI to communicate issues with unit leadership and develop a response plan. For example, if hand hygiene compliance data show a significant negative impact upon introducing the intervention, we will work with the LSI and unit leadership to educate unit staff on the importance and workflow of hand hygiene in combination with gloving practices.

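### The patient contact survey sets no minimum exposure and does not separate isolated patients, who are gloved in both arms, so an arm difference would be diluted; its targets also say *site* where *unit* is meant.

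*Combined protocol and SAP*

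**What the plan says.** Section 5.3 (Surveys, Patients) gives the survey's purpose as to "understand perceptions of whether contact with patients is impacted due to the intervention". Its list of possible ways to share the form includes "leaving the survey on bedside table, including survey in admission/discharge paperwork". The form carries no personal or health identifiers. Section 5.6 (Survey) adds the timing: "Surveys will be conducted during the patient's stay in the unit and may be returned to any member of their care team". It also lets patients hand the form in at the nursing station when they leave, and says the results will be compared between arms. Section 5.7 gives the survey a second use: "The Provider-Patient Contact survey will also be used to monitor patient responses to the intervention".

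On isolation, section 5.3 (Interviews, Patients) says of "Patients who are under contact precaution isolation above and beyond the intervention" that they will not be approached for interviews. The survey text has no matching rule, and section 5.5 lists criteria for interviews, focus groups and specimen collection but none for surveys.

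On numbers, section 5.2.3 states: "We will aim to survey 10 patients per site at all 10 participating sites, for a total of 100 patients", split 50 and 50 by arm, plus at least one environmental services worker per site for a total of 10. Section 5.3 says only: "We will aim to obtain 10 patient surveys per site", and one worker survey per site, with no totals. Section 4.2 says: "Five sites (Milwaukee, Hines, Bronx, Washington DC, Portland) will enroll ten inpatient units", two at each site.

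**The concern.** The survey asks whether contact with staff differs when staff glove for everyone. Two kinds of respondent say little or nothing about that: a patient who fills in the form soon after arrival, before much contact with unit staff, and a patient in contact isolation, whose carers wear gloves and gowns whichever arm the unit is in. Both pull the observed arm difference toward zero. In a comparison that is also used to check that gloving does not harm patient experience, a pull toward zero makes a real problem harder to see.

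The protocol already recognises the second issue elsewhere. Section 5.6 (Isolation Days of Care) warns that contact precautions in the control group could confound the endpoints, and collects isolation data for that reason. The survey has no counterpart.

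Separately, the plan counts ten sites in one place and five in another. A research assistant working from section 5.3 alone could stop at ten patients for the whole facility.

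**Working it through.** **1. The stated target.** Inputs: 10 patients per *site* and 10 *sites* (section 5.2.3); five facilities with two units each (sections 4.2 and 5.3, Intervention); one intervention and one control unit per facility (section 5.2.1).
- With ten units: 10 × 10 = 100, and 5 × 10 = 50 per arm. This reproduces section 5.2.3 exactly. For workers, 1 × 10 = 10, also as stated.
- With five facilities: 10 × 5 = 50 patients and 1 × 5 = 5 workers. Neither matches.

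So *site* in the survey targets of section 5.2.3 has to mean unit, whereas in section 4.2 it means facility.

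**2. Isolated patients.** Section 5.2.2 prescribes gowns and gloves for patients with known CDI or another MDRO on intervention units, and the same on control units. These patients therefore carry no glove contrast. Section 5.6 (Contact Precaution Compliance) expects 2-6 isolated patients on an average unit, and the average unit has 20 patients: 2/20 = 10% and 6/20 = 30%.

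Let f be the isolated share of respondents, equal in both arms, and δ the true difference in non-isolated patients. If isolated patients show no arm difference:

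observed difference = (1 − f) × δ + f × 0 = (1 − f) × δ

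- f = 0.10 gives 0.90 δ; 50 × 0.10 = 5 isolated respondents per arm, 45 not isolated.
- f = 0.30 gives 0.70 δ; 50 × 0.30 = 15 isolated respondents per arm, 35 not isolated.
- The sample needed for the same power rises by 1/(1 − f)²: 1/0.81 = 1.23 to 1/0.49 = 2.04.

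**3. What that does to power.** The plan gives no test, effect size, SD or power for the survey, so this is an illustration only. Assumptions: SD 1, two-sided 0.05, no clustering, δ = 0.5 SD, power = Φ(d × √(n/2) − 1.96), where d is the difference actually present in the group analysed.

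| Analysis | n per arm | d (SD) | Power |
|---|---|---|---|
| No isolated respondents | 50 | 0.50 | Φ(2.50 − 1.96) = 70% |
| All respondents, 10% isolated | 50 | 0.45 | Φ(2.25 − 1.96) = 61% |
| All respondents, 30% isolated | 50 | 0.35 | Φ(1.75 − 1.96) = 42% |
| Non-isolated only, 10% isolated | 45 | 0.50 | Φ(2.37 − 1.96) = 66% |
| Non-isolated only, 30% isolated | 35 | 0.50 | Φ(2.09 − 1.96) = 55% |

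Restricting to non-isolated respondents restores the full size of the difference and recovers part of the lost power.

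**4. Timing.** Section 5.3 governs how the form is handed out and allows it to travel with admission papers. Section 5.6 governs when it is done: during the unit stay, with return possible at discharge. Together they permit completion anywhere from shortly after arrival to departure. If a share e of returns came from patients with essentially no staff contact, the factor in step 2 would become (1 − f)(1 − e), taking e as independent of isolation. The documents give no basis for e, so I put no number on it.

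**5. Whether it can be mended later.** The form has no identifiers and may be returned through an anonymous receptacle. No completion time or isolation item is specified. Isolation status and time on the unit could therefore not be linked back from records.

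**The case against.** The best defence is that this is an ancillary survey in a pragmatic trial. Surveying everyone on the unit answers a legitimate unit-level question, and isolated patients are present in both arms, so neither arm is favoured. The 10-30% is a census expectation, not a share of respondents; a nurse must agree before the research assistant approaches a patient, which could lower the isolated share. No statistical reason is given for the interview exclusion, so its absence from the survey is not in itself an inconsistency. All of this stands. It limits the point to dilution and supports keeping an all-respondent comparison. It does not explain why the plan should be unable to show the non-isolated comparison at all.

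Three stronger readings are tempting, and the documents do not support them.
- *Patients will answer before any exposure.* Admission papers are one of several distribution options, paired with discharge papers, and section 5.6 places completion during the stay. A form received at admission can be filled in later. Early completion is possible and not prevented; it is not planned.
- *The target is really 50, not 100.* Section 5.2.3 fixes 100 with 50 per arm, which also requires both arms to contribute. Fifty arises only if section 5.3 is read alone and *site* is taken as facility. This is a wording conflict, not a smaller sample.
- *This is the trial's only check on patient experience, so false reassurance is likely.* Section 5.6 also plans 50 patient interviews that cover negative perceptions, and section 5.7 lists routine metrics, including satisfaction scores, that may be monitored. The interviews are held only on intervention units, so the survey remains the only patient report on experience that the study itself collects in both arms. That makes it worth protecting, but no more than that.

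**Conclusion.** The point holds as a modest design weakness in an ancillary comparison. Isolation alone would shrink a true arm difference to about 70-90% of its size. This assumes that respondents mirror the expected unit census, that the isolated share is the same in both arms, and that isolated patients show no arm difference. Early completion could add to the dilution by an amount the documents do not allow one to estimate. The direction is toward no difference, without favouring either arm. The power figures depend further on the assumed 0.5 SD, SD of 1 and absence of clustering, and serve only to show scale.

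The mixed use of *site* is a conflict to reconcile; the stated totals are right once it is read as unit. The primary outcome and the clinical secondary outcomes are not affected. The reason to act now is that neither gap can be closed once anonymous forms have been returned.

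**What to change.** - In section 5.3 (Surveys, Patients), remove the admission-paperwork route and say that the survey is given at or near discharge from the unit. Make section 5.6 (Survey) agree. The documents offer no basis for a particular minimum stay, and none is needed.
- Add one tick-box for contact-isolation status, with no identifiers. Staff could mark it before handing over the form, since section 5.2.2 already has precaution signs on each door.
- In the Statistical Analyses section (numbered 5.7.2), state that the arm comparison will be reported in non-isolated patients alongside all respondents.
- In section 5.2.3 and in both survey parts of section 5.3, replace *per site* and *10 participating sites* with *per unit* and *10 participating units*, in line with five sites and ten units. The totals remain 100 patients (50 per arm) and 10 environmental services workers.

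The cost is a wording change, one extra item on the form and slightly fewer early returns.

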### *Environmental Services Workers*

We will also recruit environmental services workers to complete a survey of their experiences with the intervention (e.g. to determine if the increased gloving impacts their workload). No PII or PHI will be included on these surveys. We will aim to obtain 1 survey per site.

We will discuss with supervisors prior to beginning any recruitment or survey procedures in order to determine the appropriate recruitment strategies for the local team and its workflow. Recruitment options include leaving an introductory flyer as well as the information sheet and survey itself in staff mailboxes. In addition, we may present the project and information sheet at regularly scheduled staff meetings where the supervisor is not present. We will provide time to answer questions as well as information for how to complete and return surveys. A discreet, anonymous receptacle will be placed for completed surveys. The survey completion should take no more than 5 minutes and thus should not interfere with work duties.

## **5.4 Informed Consent Procedures**

Verbal Informed consent and signed HIPAA authorization will be obtained for stool sample collection from the participant.

We are requesting a waiver of informed consent for the intervention (use of universal gloving) and access to unit records (patient admission and discharge; gains and loss report, VA administrative records on unit admissions and discharges) to track compliance with study procedures and measure unit-level clinical outcomes and observe healthcare worker compliance with gloving procedures. We will work with each facility to determine how they normally track admission and discharge. We anticipate that most, if not all, sites will utilize the standard gain and loss report or admission, discharge, transfer (ADT) report available on VISTA; thus, we plan to use this report to

track admission and discharge. To track unit-level clinical outcomes, we will either ask units to provide this information to us using standard reporting parameters for each site, or we will access this information via CPRS, VISTA, and/or the VA administrative records (e.g., the CDW).

We are requesting a waiver of documentation of informed consent for patient specimen collection and healthcare worker/ patient interviews, focus groups, and surveys.

We are requesting waivers of consent because:

It is not possible to carry out the study using written individual informed consent. In this study, we are performing a cluster randomized trial. Cluster randomized trials such as these most often are granted waived consent due to the inability to carry out the research without waiver of consent. As is the case for many infection control or behavioral interventions, this intervention cannot be studied using a traditional patient-level randomization because: a) the intervention is difficult if not nearly impossible to randomize to individual patients in the unit and not other patients; b) there are group-level variables in patient units (patient-specific variables and healthcare worker-specific variables) that make the CRT the most valid study design; and c) bacteria transmission does not occur on the individual level but on a group level within a patient unit. An example of a group level variable is colonization pressure. Colonization pressure, defined as the percent of patients in a given patient unit with an infectious agent such as an antibiotic-resistant organism (MRSA), affects the probability of other patients acquiring the bacteria and developing an infection (primary and secondary outcomes of the study). Since wearing gloves and gowns to care for a particular patient (e.g., patient A) would protect that patient from acquiring an infection, but would also prevent other patients (e.g., patient B, patient C, patient D) in the same unit from acquiring bacteria from patient A. Another reason is that if the study was randomized to individual patients, it is likely that healthcare workers would be influenced by the intervention of wearing gloves and gowns and potentially being more adherent to other infection control practices. A patient-level randomized trial is inadequate to study interventions that reduce transmission of infections. CRT is the preferred design in many infectious disease and infection control studies when the investigator is worried about contamination of intervention to control patients.

(1) The research involves no more than minimal risk to the participant. Use of barrier contact precautions (gloving plus gowning) is currently the standard of care for patients with certain communicable diseases including antibiotic-resistant organisms (e.g., MRSA), so the expansion of universal gloving for care of all patients (intervention) does not present additional risk to healthcare workers or patients.

(2) The waiver will not adversely affect rights and welfare of participants. Use of barrier precautions are currently the standard of care for patients with certain communicable diseases including antibiotic-resistant organisms (e.g., MRSA). It is expected of hospital accrediting standards and professional standards that equal; high quality care will be provided to all patients regardless of diagnosis. Patients on units that are in the intervention arm of the study where barrier precautions are used for all patient contacts will receive the same high-quality care as a patient in which barrier precautions are either being used for other purposes or not being used at all. Patients on units that are in the control arm of the study will have no change in their care. Educational materials used in the study will remind healthcare workers in the participating sites that patient care practices must conform to local facility standards regardless of whether barrier precautions are implemented for patient care.

(3) Whenever appropriate, additional pertinent information will be provided to participants after participation. In the event that patients or healthcare workers request study information, each site will have readily available copies of the study information sheet which describes the purpose of the trial, the procedures involved in the trial, and who to contact for further information. No individual patient information will be provided.

